5.1. Disposition

Subject disposition will be summarized for the FAS. A disposition of subjects includes the number and percentage of subjects for the following categories:

- Subjects who were randomized
- Subjects who completed the treatment
- Subjects who discontinued the treatment
- Subjects who completed the study
- Subjects who discontinued from the study

The reason for study discontinuation will also be summarized.

A summary of the subjects included in each analysis set will be presented.

All percentages will be based on the number of subjects in the FAS.

Subject disposition data will also be presented in a listing.

5.2. Protocol Deviations

Significant protocol deviations will be summarized by deviation type for all FAS subjects. A listing of all protocol deviations will be provided as well. Prior to DBL, the listing for protocol deviations will be determined in a blinded manner.

6. Demographics and Baseline Characteristics

6.1. Demographics

A summary of demographics and baseline characteristics will be presented. The demographic characteristics will consist of age (years), sex, race, and ethnicity. The baseline characteristics will consist of baseline height (cm), baseline weight (kg), and baseline body mass index (BMI)

(kg/m²). Body mass index is calculated as (body weight in kilograms) / (height in meters)². Age, baseline height, baseline weight, and baseline BMI will be summarized using descriptive statistics. The number and percentage of subjects by sex (Male, Female), race (White, African American, Asian, American Indian or Alaska Native, Native Hawaiian or Other Pacific Islander, and Other) and ethnicity (Hispanic or Latino, Not Hispanic or Latino) will also be reported. Percentages will be based on the total number of subjects in the FAS. A separate presentation may be done for the Safety Analysis Set.

Subject demographic and baseline characteristics will also be presented in a listing.

6.2. Baseline Disease Characteristics

Baseline disease characteristics include the following parameters:

- FSHD repeat number (1, 2, 3, 4, 5, 6, 7, 8, and 9)
- FSHD repeat category (1 to 3 repeats, 4 to 9 repeats)
- Clinical severity score (RICCI score 2, 2.5, 3, 3.5, 4)
- FSHD history
 - Age of symptom (years)
 - First symptom
 - Weakness
 - Difficulty smiling
 - Reaching over head
 - Walking
 - Running
 - Keeping up with peers
 - Pain
 - Others
 - Age at diagnosis (years)
 - Pain related to FSHD

Percentages will be based on the total number of subjects in the FAS. Listings will be presented for the FAS. A separate presentation may be done for the Safety Analysis Set.

6.3. Medical History

Medical history will be coded using the Medical Dictionary for Regulatory Activities (MedDRA) Version 22.0 or higher. The number and percentage of subjects with any medical history will be summarized by treatment group and overall and presented by system organ class (SOC) and preferred term (PT). Percentages will be calculated based on the number of subjects in the FAS.

Subject medical history data including specific details will also be presented in a listing.

7. Treatments and Medications

7.1. Prior and Concomitant Medications

All medications used within 28 days prior to the date of screening through safety follow-up will be collected on the CRF (case report form). All medications will be coded according to the World Health Organization Drug Dictionary (WHODD Global B3 Mar 2019 or higher).

A prior medication is defined as any medication that is taken prior to the first dose of study drug and stopped before the date of study drug administration. A concomitant medication is defined as any medication that is taken on or after the date of study drug administration regardless when the medication is started up to 7 days after the last dose date.

For the purpose of inclusion in prior and/or concomitant medication tables, incomplete medication start and stop dates will be imputed as follows:

Missing start dates (where UK, UKN, and UNKN indicate unknown or missing day, month, and year, respectively):

- UK-MMM-YYYY: If the month and year are different from the month and year of administration of study drug, assume 01-MMM-YYYY. If the month and year are the same as the administration of study drug month and year and the end date (after any imputation) is on or after the administration of study drug, then assume the first day of the month of the administration of study drug. If the month and year are the same as month and year of the study drug administration and the end date (after any imputation) is prior to the study drug administration, then assume the first day of the month of the administration of the study drug for the start date;
- DD-UKN-YYYY/UK-UKN-YYYY: If the year is different from the year of the study drug administration, assume DD-JAN-YYYY/01-JAN-YYYY of the collected year. If the year is the same as study drug administration year and the end date (after any imputation) is on or after the study drug administration, then assume the date of the study drug administration. If the year is the same as the study drug administration and the end date (after any imputation) is prior to the first dose of study drug, then assume the first day of the month of the administration of the study drug for the start date.

Missing stop dates (where UK, UKN, and UNKN indicated unknown or missing day, month, and year, respectively):

- UK-MMM-YYYY: Assume the last day of the month;
- DD-UKN-YYYY: Assume DD-DEC-YYYY;
- UK-UKN-YYYY: Assume 31-DEC-YYYY.

If the start date is completely missing and end date is not prior to the study drug administration, then the medication will be classified as concomitant. If the start date is completely missing and the end date is within 30 days prior to the first dose of study drug, then the medication will be

classified as prior. If the end date is missing, then the medication will be classified as ongoing. Medications for which the start and end dates are missing will be classified as concomitant.

Prior and concomitant medications will be summarized by Anatomical Therapeutic Chemical (ATC) classification level 4 and preferred drug name, respectively. When ATC classification level 4 is missing, the next available ATC level will be used as ATC level 4.

Summaries will be performed using the Safety Analysis Set.

Data on prior and concomitant medications will also be presented in a listing.

7.1.1. Prior Medications

The total number of prior medications and the number and percentage of subjects with at least one prior medication will be summarized by treatment group and overall. The number and percentage of all prior medications will be summarized by treatment group and overall and presented by Anatomical Therapeutic Chemical (ATC) level 4 and PT. All summaries will be performed using the FAS.

7.1.2. Concomitant Medications

The total number of concomitant medications and the number and percentage of subjects with at least one concomitant medication will be summarized by treatment group and overall. The number and percentage of all concomitant medications will be summarized by treatment group and overall and presented by Anatomical Therapeutic Chemical (ATC) level 4 and PT. All summaries will be performed using the Safety Analysis Set.

7.2. Study Treatments

7.2.1. Extent of Exposure

Duration of exposure is defined as the total number of days a subject is exposed to study drug and will be presented as the total number of days from the first dose date (Day 1) to the last dose date (ie, calculated as the date of last dose minus the date of first dose + 1). If the last dose date is missing, or if a subject is lost to follow-up, but the drug accountability log confirms that the subject has taken study drug, the visit date following the last completed drug accountability log will be used.

The exposure to study drug will also be characterized by cumulative dose, which is defined as the cumulative number of tablets taken.

The duration of exposure to study drug by treatment group will be summarized for all subjects in the Safety Analysis Set and will be presented in a table using summary statistics. The duration of exposure will then be classified into one of the following categories: < 8 weeks, \geq 8 weeks, \geq

16 weeks, \geq 24 weeks, \geq 36 weeks and \geq 48 weeks and will be presented as the number and percentage of subjects in each duration category. Percentages will be computed from the number of subjects in the Safety Analysis Set.

The total cumulative dose in mg will be defined as the total number of tablets taken across all study days times 7.5 mg. Average daily dose will be defined as cumulative dose divided by total days on study drug. The average daily dose and cumulative dose will be summarized using summary statistics.

A summary of each subject's exposure will also be presented in a listing.

7.2.2. Treatment Compliance

Study drug compliance will be calculated for each subject by taking into account whether a subject takes all doses of study drug as instructed. The number of tablets taken will be calculated by subtracting the number of tablets returned from the number of tablets dispensed.

The study drug compliance (%) for each visit will be calculated by dividing the total number of tablets taken up to the next visit by the total number of tablets prescribed at each visit and then multiplying by 100. Compliance (%) = [(total number of tablets dispensed – total number of tablets returned) / (number of days in visit interval * number of tablets prescribed per day)] * 100. The overall study drug compliance (%) will be calculated by dividing the total number of tablets taken at all visits by the total number of tablets prescribed for all visits and then multiplying by 100.

The overall study drug compliance will be summarized by treatment group.

The number and percentage of subjects in different percentage compliance categories (<80%, \geq 80% to $<$ 120%, and \geq 120% compliant) will be presented. Percentages will be calculated from the number of subjects in the Safety Analysis Set.

8. Efficacy Analysis

Efficacy endpoints will be analyzed using the FAS. The primary efficacy endpoint will also be performed on the PPS and will be considered supportive of the primary analyses on the FAS. As part of sensitivity analysis, a separate analysis will be done of efficacy endpoints using the Open-label Losmapimod (Pre-COVID-19) Analysis Set.

8.1. Hypothesis Testing Procedure for Key Study Endpoints

A fixed sequential testing procedure will be used to control for the experiment-wise Type I Error to test the following key study endpoints as ordered below:

- DUX4 change from baseline at Week 16 or Week 36 [DUX4 Score 1. See [Section 8.2](#)]
- LMV change from baseline at Week 48 [Total LMV, composite of assessments from multiple muscles. See [Section 8.3](#)]

- FSHD TUG change from baseline at Week 48 [average completion time of FSHD TUG. See [Section 8.4.2](#)]

At each step in this sequential ordering, statistical significance for the endpoint will be claimed only if the p-value for the test is less than the final alpha obtained from the O'Brien-Fleming Spending Function ([Table 12-1](#)) and the p-values for the tests for all previous endpoints in the list are also less than the final alpha provided.

The testing hierarchy will be as follows:

- If the p-value for the test of the comparison of DUX4 change from baseline between the two treatment groups is less than the final alpha, then the comparison of the LMV change from baseline will be conducted. If the p-value from this comparison is also less than the final alpha, then the comparison of the FSHD TUG change from baseline will be conducted.
- Once a p-value is greater than or equal to the final alpha for the current endpoint being evaluated, then only the tests for the preceding endpoints will be considered significant.
- The formal statistical tests for any of the endpoints will be considered statistically nonsignificant when the test has a p-value of greater than or equal to final alpha. However, nominal p-values will still be provided for these endpoints.

8.2. Change from Baseline in DUX4 Activity in Skeletal Muscle at Week 16 or Week 36

A subset of DUX4-gene transcripts will be measured in skeletal muscle biopsies, using a validated QRT-PCR assay, to assess the treatment effect of losmapimod over placebo on aberrant DUX4 activity. A mean DUX4 score (DUX4 Score 1) will be derived for each patient, at each time point based on normalized gene expression values for the panel of pre-selected genes. DUX4 Score 1 is a mean of normalized (delta-CT) for the pre-selected panel of 6 genes, by subject, for each timepoint.

The quantification of gene expression and normalization of qPCR are conducted at a central laboratory (Q2 Lab Solutions) in a blinded fashion, with no access to treatment assignment information. A total of six DUX4-regulated gene transcripts (CCNA1; KHDC1L; MBD3L2; PRAMEF6; SLC34A2; ZSCAN4) have been pre-selected for inclusion in the mean DUX4 score. DUX4 Score 1 will be used for the primary analysis. A second and third composite scores (DUX4 Score 2 and DUX4 Score 3, respectively) will be used for sensitivity analysis. For details on assay validation, gene subset selection criteria/process, and derivation of DUX4 Score, see [Appendices 15.1 – 15.5](#).

DUX4 score 1 will be summarized as change from baseline to either Week 16 or Week 36. Study subjects can only have one post-baseline biopsy (either Week 16 or Week 36, but not both). If the pre-treatment or on-treatment DUX-4 results are unavailable, then the assessment is considered missing. See [Section 8.2.1](#) for details of missing data handling for DUX4 Score.

For each treatment, descriptive statistics of aberrant DUX4 activity will be presented at Baseline and post-baseline (Week 16 or Week 36) as well as change from baseline. An ANCOVA model

will be used to analyze the change from baseline in DUX4 activity in affected skeletal muscle, which is the response variable, with repeat number category and treatment group as fixed effects and baseline DUX4 activity in affected skeletal muscle as a covariate. Within-group least-squares (LS) means, the associated standard errors (SEs) and 2-sided 95% CIs, treatment differences in LS means and the associated 2-sided 95% CIs and 2-sided p-values will be derived from the model and presented in the table. If the model-based p-value of the treatment difference in the change from baseline is less than the final alpha provided in [Table 12-1](#), the difference between two treatment groups will be determined to be statistically significant.

Similar methods will be used to analyze the change from baseline in DUX4 activity within subgroups identified in [Section 4.6](#) to evaluate consistency of treatment effects across the subgroups. For the repeat category subgroup analysis, the repeat category will be excluded as fixed effect from the model.

The LS mean change from baseline by visit of the DUX4 activity will be graphically presented.

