3.1. Overall Study Design and Plan

This study will be conducted in 2 parts: a randomized, double-blind placebo-controlled treatment period for 48 weeks, followed by a losmapimod open-label treatment period with a study population of males and females between 18 and 65 years of age at enrollment, inclusive, who have confirmed diagnosis of FSHD1 with 1 to 9 repeats via assessment of the size of the D4Z4 array on chromosome 4; a clinical severity score of 2 to 4 (RICCI score; range 0-5), inclusive, at screening; and a MRI eligible muscle for biopsy, as determined by a central reader.

During the placebo-controlled treatment period, approximately 76 subjects with FSHD1 will be randomized 1:1 to receive 15 mg PO of losmapimod (n=38) or placebo (n=38) tablets BID for 48 weeks. At the time of the latest protocol amendment (Version 4.0; 10Apr2020), enrollment was completed, a total of 80 subjects have been enrolled.

Once subjects reach Week 48, they will have the option to roll over into the open-label extension, with all subjects receiving 15 mg losmapimod PO BID. Subjects who wish to roll over into the

open-label extension must complete all procedures from the Week 48 end of placebo-controlled treatment period/start of open-label extension visit. Prior to the COVID-19 pandemic, subjects who reached the Week 24 visit had the option to roll over into the OLE. Subjects who have already rolled over to the OLE prior to the COVID-19 pandemic (n=12) will remain on open label treatment. Their next clinic visits will follow the assessments for the Week 36 and Week 48 visits in the placebo-controlled portion of the study in the COVID-19 Pandemic Emergency protocol version 4.0. These subjects will not undergo the Week 36 biopsy. Subjects who did not roll over prior to the COVID-19 pandemic, and thus are still on the randomized treatment, will continue on the randomized treatment and roll over into the OLE at the Week 48 visit. Please see the COVID-19 Pandemic Emergency protocol version 4.0 for further details.

[figure not shown]
The placebo-controlled treatment period will include a 4-week screening period and a 24 or 48-week placebo-controlled treatment period. Subjects who rolled over to the OLE portion of the study prior to the COVID-19 pandemic (under protocol version 3.0) have completed a 4-week screening period followed by a 24-week placebo-controlled treatment period.

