4.6. Subgroup

A subgroup analysis will be performed for the following subsets at baseline:

- 1) Repeat category (1 to 3 repeats, 4 to 9 repeats)
- 2) Clinical severity score (RICCI score 2 to 3, 3.5 to 4)

- 3) Sex (Male, Female)
- 4) Fat Fraction at biopsy site. This is an average of results from 2 Readers.
 - a. > 10 to <=20%
 - b. >20 to <=40%
- 5) Mean DUX4 score (DUX4 Score 1) at baseline values partitioned by 3 thresholds:
 - a. >=Q1 (first quartile of observed mean DUX4 score (DUX4 Score 1) at baseline)
 - b. >=Q2 (median of observed mean DUX4 score (DXU4 Score 1) at baseline)
 - c. >=Q3 (third quartile of observed mean DUX4 score (DXU4 Score 1) at baseline)
- 6) Subjects completing 'RWS protocol with above shoulder movements' at baseline
- 7) Subjects who completed 'RWS protocol with above shoulder movements' all through the study
- 8) Subjects completing the classical TUG, without an assisted device, at baseline
- 9) Subjects completing the FSHD TUG, without an assisted device, at baseline
- 10) MFF_{tot}, LMV_{tot} and MFI_{tot} with thresholds at the median of observed baseline data
- 11) Subjects with non-censored laboratory observations for DUX4 score at baseline.

Endpoints for which the subgroup analysis will be performed are indicated in subsequent sections.

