4.7. Sample Size

Assuming an effect size of 0.70, a sample size of 68 subjects (34 subjects per group) will be needed to provide 80% power with a 2-sided test at a 0.05 significance level to detect a difference between losmapimod and placebo in change from baseline in DUX4 activity in affected skeletal muscle after 16 weeks or 36 weeks (depending upon when the muscle biopsy was performed) during the placebo-controlled treatment period. Assuming that approximately 10% of subjects will be non-evaluable, approximately 76 subjects will be randomly assigned at a 1:1 ratio to losmapimod and placebo (38 subjects per group).

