8.3. MSK MRI Muscle Fat Fraction, Lean Muscle Volume and Muscle Fat Infiltration

Measurement of the extent of skeletal muscle tissue replacement by fat in FSHD patients will be done through automatic skeletal muscle segmentation for the 3D muscle volumes and fat fraction analysis via robust algorithms using Dixon imaging. This will be assessed at Screening, Week 12, and Week 48.

A. Composite measures: Composite variables, incorporating pre-selected muscles, will be derived for longitudinal analysis of muscle fat fraction, lean muscle volume and muscle fat infiltration (MFF_{tot} , LMV_{tot} , and MFI_{tot} respectively), as described in [Appendix 15.6](#). The scores will be derived by scientists at the MRI Service Provider (AMRA Medical Inc.) in a blinded fashion, with no access to treatment assignment information.

For each treatment, descriptive statistics of MFF_{tot} , LMV_{tot} , and MFI_{tot} per visit as well as changes from baseline will be presented. A Mixed Effect Model for Repeated Measures (MMRM) model will be used to analyze the change from baseline in each composite MRI score, with repeat number category, treatment group, visit, and treatment-by-visit interactions as fixed effects and baseline value of the parameter as a covariate. Within-group LS mean changes from baseline, the associated SEs and 2-sided 95% CIs, treatment differences in LS mean changes from baseline at Weeks 12 and 48 and the associated 2-sided 95% CIs and 2-sided p-values will be derived from the MMRM model and will be provided in the summary table. An unstructured covariance matrix will be used to model the correlation among repeated measurements within each subject. If models using unstructured covariance do not converge, an AR(1) covariance structured will be used instead. **LMV_{tot} is the key endpoint for hypothesis testing.**

B. Individual Muscles: For each muscle location, a similar method will be used to analyze muscle fat fraction (%), lean muscle volume (L), and muscle fat infiltration (%) per visit as well as changes from baseline.

The LS mean change from baseline by visit of the MSK MRI muscle fat fraction, lean muscle volume, and muscle fat infiltration will be graphically presented.

The change from baseline in the composite parameters will also be summarized by subgroups identified in [Section 4.6](#) to evaluate consistency of treatment effects across the subgroups.

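### SAP 8.2 sets out to assess consistency of the DUX4 effect across subgroups but plans only separate within-subgroup models, with no estimate of the difference in effect between levels

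*SAP*

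**What the plan says.** SAP 4.6 states "A subgroup analysis will be performed for the following subsets at baseline" and lists eleven items. Some are two-level splits: repeat category, RICCI score, sex, fat fraction at the biopsy site, and median splits of the MRI composites. Item 5 is three nested sets of baseline DUX4 score (at or above the first quartile, the median and the third quartile). Item 11 is a single subset. Items 6 to 9 were single subsets; addendum section 3.2 recasts them as two levels shown side by side. Item 7 depends on completion throughout the study, so it is not a baseline factor.

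For DUX4, SAP 8.2 says "Similar methods will be used to analyze the change from baseline in DUX4 activity within subgroups identified in" Section 4.6, in order to evaluate consistency. The method carried over is the primary ANCOVA, with LS mean differences, 95% CIs and two-sided p-values. Repeat category is dropped from the model in its own subgroup analysis, which confirms that the levels are fitted separately.

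For the MRI composites, SAP 8.3 says only "The change from baseline in the composite parameters will also be summarized by subgroups identified in" Section 4.6, again for consistency. It names no subgroup model and no subgroup p-value.

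The only treatment interactions anywhere in the protocol, SAP and addendum are with visit or time. In SAP 15.8 all thirteen DUX4 subgroup tables (14.2.2.1.2 to 14.2.2.1.14) are flagged for topline and six of them for the interim. SAP 12 sends the interim DUX4 subgroup results to the sponsor with p-values.

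**The concern.** Consistency is a question about the difference in treatment effect between levels. The planned output gives each level's effect against zero and leaves the difference unestimated. With this sample size each level is underpowered, so a p-value below 0.05 in one level and above it in the other is an expected result of a uniform effect and carries little information about heterogeneity.

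At stake is interpretation of the topline and interim packages. A reader could conclude that losmapimod lowers DUX4 activity in one kind of patient and not in another when the effect is the same. The primary test is not affected.

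**Working it through.** **Inputs.** From SAP 4.7: "Assuming an effect size of 0.70, a sample size of 68 subjects (34 subjects per group) will be needed", where the design target is "80% power with a 2-sided test at a 0.05 significance level". The same section allows 10% for patients without evaluable data and plans 76 randomized, 38 in each arm. From SAP 3.1: "a total of 80 subjects have been enrolled". Subgroup proportions are not in the documents, so a range is shown. The median splits of the MRI composites are close to even by construction.

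**The plan's own figure.** A two-sample noncentral-t calculation at d = 0.70 and two-sided 0.05 gives 79.97% power at 33 per arm and 81.2% at 34, so 34 is the smallest n per arm that reaches 80%. Then 68 / 0.90 = 75.6, or 76 after rounding up. The stated sample size is reproduced.

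**Power within levels, uniform effect of 0.70.** Let p1 and p2 be the noncentral-t power in two disjoint levels, with equal SDs and 1:1 allocation within each.

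- P(exactly one significant) = p1(1 − p2) + p2(1 − p1).
- Even split, 17 per arm per level: p1 = p2 = 0.508. Exactly one: 2 × 0.508 × 0.492 = 0.500. Both: 0.508² = 0.258. Neither: 0.492² = 0.242.
- 25/75 split, 8.5 and 25.5 per arm: p1 = 0.272, p2 = 0.688. Exactly one: 0.272 × 0.312 + 0.688 × 0.728 = 0.586.

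| Smaller level's share | P(exactly one significant) |
|---|---|
| 50% | 50% |
| 33% | 54% |
| 25% | 59% |
| 15% | 66% |
| 10% | 71% |

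**Sensitivity, even split.**

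- With 76 or 80 evaluable in total, the rate is 49%.
- At the final alphas in SAP Table 12-1 it stays at 50%.
- Given a significant overall result, it is 57% (100,000 simulated trials).
- It depends on the true effect: 23% at 0.3, 41% at 0.5, 31% at 1.0, and 9.5% with no effect.
- At the interim with 22 to 32 pairs it is 30% to 38% if levels are tested at 0.05. At the interim alphas of 0.000567 and 0.004027 it is about 1% and 9%.

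**Interaction test.** In the same simulations a treatment-by-subgroup test at 0.05 flagged the uniform effect 4.9% to 5.0% of the time, for smaller-level shares of 15% to 50%.

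**Precision of the interaction, in SD units.** SE = sqrt(2/n1 + 2/n2), and t on 64 df is 1.998.

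- Even split: sqrt(2/17 + 2/17) = 0.485; half-width 0.485 × 1.998 = 0.97.
- 25/75 split: sqrt(2/8.5 + 2/25.5) = 0.560; half-width 0.560 × 1.998 = 1.12.

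Power of the interaction test at an even split is 29% for effects of 0.35 against 1.05, and 81% for 0 against 1.40.

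**The case against.** A reader might infer that the SAP decides consistency by within-subgroup p-values. It does not: SAP 8.2 sets no criterion and reports estimates and CIs beside the p-values. The 50% is the error rate of one reading. Judged by direction alone, a uniform effect of 0.70 gives opposite signs only about 4% of the time at an even split. This stands, and the rate must be stated conditionally. The reading is still a likely one, because the reused ANCOVA carries a significance rule and the interim tables are supplied with p-values.

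A reader might also extend the 50% to MRI. The documents do not support that. SAP 8.3 promises summaries only, no MRI effect size is given, and the MRI subgroup tables are flagged neither for topline nor for the interim. Only the missing interaction carries over.

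A third tempting inference is that subgroup results could drive interim stopping. The stopping criterion in SAP 12 concerns the primary endpoint and names no subgroup.

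It is fair to add that, for disjoint levels, a reader could take the difference between the two reported effects and combine their SEs by hand. The ingredients are there; the estimate is simply not planned. SAP 8.1 also confines formal testing to three overall endpoints, so no confirmatory claim rests on subgroups. Finally, the two-level calculation does not fit the nested baseline-DUX4 sets, item 11 or item 7.

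**Conclusion.** The point holds for DUX4. SAP 8.2 names consistency as its aim and plans separate fits with p-values but no treatment-by-subgroup estimate. If the tables are read as significant versus not, a uniform effect of 0.70 with 34 evaluable per arm shows exactly one of two levels significant 50% of the time at an even split and 59% at 25/75, against 5% for an interaction test. At an even split the figure is 23% to 41% for true effects of 0.3 to 0.5, and 31% at 1.0. These figures assume two disjoint levels, equal SDs, 1:1 allocation within levels, and subgroup proportions that the documents do not give.

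For MRI the gap is the same missing estimate, with no derivable error rate. This is a cheap improvement to interpretation; the primary analysis stands as written.

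**What to change.** In SAP 8.2, for each two-level baseline factor, fit one ANCOVA on the whole FAS, adding subgroup and treatment-by-subgroup to the primary model. For repeat category, already in the model, only the interaction is new. Report each level's treatment effect and the interaction estimate, all with 95% CIs and labelled exploratory. State that within-subgroup p-values are not used to judge consistency. Replace the nested baseline-DUX4 cut-offs with a continuous baseline-by-treatment term. Items 7 and 11 fall outside this change.

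In SAP 8.3, add the same interaction estimate at Week 48 from the MMRM, through a treatment-by-visit-by-subgroup term and its lower-order terms.

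The cost is SAP wording and, for DUX4, one or two terms per model. There are two downsides. Level estimates will share a pooled residual variance. The interaction interval will be wide, about ±0.97 SD at an even split and ±1.12 SD at 25/75, which exceeds the planned effect of 0.70. It is therefore descriptive only and should not serve as a gatekeeping test.
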